**Part 3A: Maximum Tolerated Dose Determination**

Similar to the MTD determination in monotherapy parts, at the end of dose escalation, the cumulative number of subjects who experience a DLT at each dose level will be used to estimate the MTD using isotonic regression as the dose with the smaller difference of estimated toxicity rate and the target DLT rate (29%), among the doses used. For DLT, see [Section 4.5.1](#).

Once the safety (during DLT evaluation) of a dose level has been determined, additional subjects may be added at that dose, to better characterize the PK, safety, and PD profile.

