Decisions to escalate, add more subjects to the current dose, de-escalate, or de-escalate and declare the current dose as unacceptable (exceeding the MTD), will be based on the rate of DLTs in evaluable subjects within the 21-day DLT evaluation period for Part 1A guided by the mTPI model and posterior inference (Figure 3.1.1-1 and Appendix 1). At least 2 DLT-evaluable subjects treated at each of the lowest 2 dose levels and at least 3 DLT-evaluated subjects treated at each of the other dose levels are required to enable decision making. Subjects with insufficient data to establish safety during the DLT evaluation period at the dose tested (eg, omitted or reduced doses for reasons other than a DLT) may be replaced upon agreement of the BMS Medical Monitor and investigators.

[figure not shown]
In addition, if dose modifications for ocular toxicity occur in 2 or more subjects within the first 5 subjects treated on study, or if with greater patient numbers > 20% of subjects require a dose modification due to ocular toxicity, enrollment will be suspended at all dose levels equal to or greater than the lowest dose level with a dose modification due to ocular toxicity, in order to assess the safety data. Enrollment may continue at lower dose levels where no dose modifications have occurred due to ocular toxicity while this safety assessment is being conducted.

There will be no intrasubject dose escalation of BMS-986148.

Figure 3.1.1-1 shows examples of scenarios guiding decision making that may be encountered during dose escalation with respect to the number of DLT evaluable subjects and the number of subjects with a DLT. All potential combinations of the number of DLTs and number of treated subjects evaluable for DLT are shown in Appendix 1. In addition to escalation or expansion decisions, dose re-escalation is permitted as per Figure 3.1.1-1 and Appendix 1 after a decision to de-escalate is made, except when a dose has been identified as exceeding the MTD. Therefore, a dose level could be revisited multiple times under the mTPI design.

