**Figure 3.1.1-1: Dose Escalation Algorithm**

a Treat 2 subjects initially if no DLTs in Dose Level 1 and criteria for transitioning from 100% increment to Fibonacci is not met; treat 3 to 4 subjects initially, otherwise.

b At the same dose, decision making based on other combinations of k/n are shown in [Appendix 1](#).

c Treat the next cohort of subjects at the next higher dose.

d Treat 3 more subjects at the current dose.

e Treat 3 more subjects at the next lower dose.

f Unacceptable current dose. Do not re-escalate to this dose.

DLT: dose-limiting toxicity; k: cumulative number of subjects who experienced DLT; MTD: maximum tolerated dose; n: cumulative number of DLT evaluable subjects; QW: every week; Q3W: every 3 weeks.

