### Part 1A: Maximum Tolerated Dose Determination

At the end of dose escalation, the MTD will be selected as the dose with the smaller difference of estimated toxicity and the target DLT rate (27%), among the doses used, with isotonic regression modeling of the accumulated DLT data based on the mTPI design.

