### **Part 1B: Maximum Tolerated Dose Determination**

Similar to the MTD determination in Part 1A, at the end of dose escalation, the MTD will be selected as the dose with the smallest difference of estimated toxicity and the target DLT rate (27%), among the doses used. See Section 4.5.1 for more information about DLTs.

Once the safety (during DLT evaluation) of a dose level has been established (Part 1A and/or Part 1B), additional subjects may be added at that dose to better characterize the PK, safety, and PD profile.

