##### **Dose Escalation Decision Rules**

A similar mTPI design as in Part 1A will be used to guide dose escalation decisions and to select the MTD. A DLT target rate of 29% (EI = 28% to 31%) will be utilized for combination treatment to guide escalation decisions. Dose escalation decisions will be based on the total number of subjects in a dose level who were DLT evaluable and the number of DLTs, guided by the mTPI Bayesian model and posterior inference.

The number of subjects at the initial cohort of all dose levels in Part 3A will be 3 to 4. A fourth subject may be enrolled in a dose escalation cohort following agreement between the investigator and the BMS Medical Monitor if able to start the first day of dosing within approximately

1 week of the third subject in the same dose escalation cohort. The DLT evaluation period will be 21 days. Enrollment of additional cohorts at the same dose level will proceed in sample sizes of up to 3 or 4 subjects. Subsequent dose levels will follow similar cohort enrollment size and decision rules. At least 3 DLT-evaluable subjects treated at each of the dose levels in Part 3A will be required to enable a decision to escalate, add more subjects to the current dose level, or de-escalate and declare the current dose as unacceptable (exceeding the MTD). Subjects with insufficient data to establish safety during the DLT evaluation period at the dose tested (eg, omitted or reduced doses for reasons other than a DLT) may be replaced upon agreement of the BMS Medical Monitor and investigators.

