**Table 3.1.3.1-1: Dose Escalation Decision Guide in Combination with Nivolumab**

		Number of DLT Evaluable Subjects at a Dose Level									
		3	4	5	6	7	8	9	10	11	12
N of DLT at a dose level	0	E	E	E	E	E	E	E	E	E	E
	1	S	S	S	E	E	E	E	E	E	E
	2	D	S	S	E	S	S	S	S	E	E
	3	DU	DU	D	E	S	S	S	S	S	S
	4		DU	DU	DU	D	D	S	S	S	S
	5			DU	DU	DU	DU	DU	D	S	S
	6				DU	DU	DU	DU	DU	DU	D
	7					DU	DU	DU	DU	DU	DU
	8						DU	DU	DU	DU	DU
	9							DU	DU	DU	DU
	10								DU	DU	DU
	11									DU	DU
12										DU	

DLT: dose-limiting toxicity; E: escalate to next higher dose level; D: de-escalate to the next lower dose level; S: stay at the current dose level; DU: unacceptable dose level, not to be re-visited.

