## **APPENDIX 2            SIMULATIONS OF MTPI VS 3 + 3 DOSE ESCALATION DESIGNS**

### **1                    SIMULATIONS FOR MONOTHERAPY DOSE ESCALATION, WITH 6 DOSE LEVELS**

Simulations of mTPI and 3+3 designs, as shown below, demonstrate that the mTPI design has a greater chance of selecting the correct MTD than the 3+3 design, and treating fewer subjects at sub-optimal doses.

The mTPI uses a set of decision rules guided by simple Bayesian models and requires a clinically relevant pre-determined target DLT rate and an equivalence interval (EI), within which any dose is considered close to the true maximum tolerated dose (MTD). For this study, the selected target toxicity (DLT) rate is 27% and EI [25%, 29%].

The mTPI design makes decisions using the same two observed numbers as the traditional 3+3 design, the number of DLT evaluable subjects and the number of subjects with DLT. Based on these two numbers, unit probability mass is calculated within each of three regions as stated above, and decision is based on which region has the largest unit probability mass:

- E: escalating to the higher dose if interval (0, 25%) has the largest unit probability mass,
- S: staying at the same dose if interval [25, 29%] has the largest unit probability mass,
- D: de-escalating to the lower dose if interval (29, 100%) has the largest unit probability mass.

At the end of the trial, MTD will be picked, by isotonic regression estimation method, to be the dose whose estimated toxicity rate is closest to the target toxicity rate among all the tried doses.

Simulations were performed to examine the performances of mTPI and 3 + 3 design for this study. Escalation decisions based on the mTPI are shown in the protocol. Decisions based on the 3+3 design are shown below:

- E: no subject with DLT out of 3 DLT evaluable subjects initially, or at most 1 subject with DLT out of 6 DLT evaluable subjects after adding 3 more subjects.
- S: 1 subject with DLT out of 3 DLT evaluable subjects initially.
- D: at least 2 subjects with DLT out of 3 DLT evaluable subjects initially, or at least 2 subjects with DLT out of 6 DLT evaluable subjects after adding 3 more subjects

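### The MTD rule does not exclude a dose already closed as exceeding the MTD; read literally, it can in rare cases name one

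*Protocol*

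**What the plan says.** **Selection.** Protocol Section 3.1.3.1 (Part 3A) takes "the dose with the smaller difference of estimated toxicity rate and the target DLT rate (29%), among the doses used". Section 3.1.1 selects for Part 1A "among the doses used, with isotonic regression modeling of the accumulated DLT data based on the mTPI design" and for Part 1B "the dose with the smallest difference of estimated toxicity and the target DLT rate (27%), among the doses used". The synopsis repeats these rules. Appendix 2, Section 1, describes the selected dose as the one "closest to the target toxicity rate among all the tried doses". The SAP has no MTD-selection rule; its Section 5 mentions the mTPI decision rules only to explain why the number per dose level cannot be fixed.

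**Closing a dose.** One of the Part 3A decisions is to "de-escalate and declare the current dose as unacceptable (exceeding the MTD". The legend of Table 3.1.3.1-1 reads "DU: unacceptable dose level, not to be re-visited". For monotherapy, a footnote to Figure 3.1.1-1 says "Unacceptable current dose. Do not re-escalate to this dose", and Section 3.1.1 permits re-escalation "except when a dose has been identified as exceeding the MTD".

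**Link between the two.** The decision-rule paragraphs of Sections 3.1.1 and 3.1.3.1 both say that the mTPI design governs the choice of MTD as well as escalation.

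**The concern.** The closing rule and the selection rule use different sets of doses. The first removes a DU dose from further dosing as above the MTD. The second picks the estimate nearest the target among every dose given. Nearest to target is a two-sided criterion: if the lower dose has no DLTs, its estimate is a full target-width too low, and a closed dose that overshoots by slightly less wins. An analyst programming the selection sentence as written would then report as MTD a dose the protocol calls unacceptable. The MTD caps the expansion dose in Parts 2 and 3B, so this is a safety decision.

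**Working it through.** **Inputs.** Part 3A target 29%, cohorts of 3 to 4, about 12 evaluable subjects over two doses (Sections 3.1.3.1 and 8.1); decisions as printed in Table 3.1.3.1-1; true DLT rates from Appendix 2, Section 2. Monotherapy: target 27%, Appendix 1 table, limits of 13 per dose and 30 in total (Section 3.1.1).

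**Assumptions.** The estimate is the observed proportion k/n, pooled only if out of order. Ties go to the dose that is not closed. D or DU at dose 1 ends the trial, as in Appendix 2.

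**1. The plan's own table.** The prior and the DU cut-off are not stated. I assumed Beta(1,1), with DU when P(rate > 29%) exceeds 0.95. For 5/9 the posterior is Beta(6,5), and P(rate ≤ 0.29) = P(Bin(10, 0.29) ≥ 6) = 0.040. So P(rate > 0.29) = 0.960, which gives DU as printed. These settings reproduce 83 of the 85 cells, including every DU cell. The exceptions are 2/6 and 3/6 (printed E, computed S).

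**2. Which closed doses can win in Part 3A.** If the lower dose has no DLTs, its distance is 0.290, so a DU dose wins only if k/n < 0.58. From 6 subjects on, the lowest DU proportions are 4/6 (0.667), 5/7 (0.714), 5/8 (0.625), 5/9 (0.556), 6/10 (0.600), 6/11 (0.545) and 7/12 (0.583); with fewer subjects they are higher still. Only 5/9 and 6/11 qualify, and 6/11 leaves one of 12 subjects for the lower dose. The only pattern is 0/3 with 5/9:
- 0.8 mg/kg: |0 − 0.29| = 0.290
- 1.2 mg/kg: |0.556 − 0.29| = 0.266, so this closed dose is named.

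**3. How often.** Worked case: true rates 0.27 and 0.45, cohorts of 3, enrolment continuing after E at 1.2 mg/kg. P(0/3) = 0.73³ = 0.389. At 1.2 mg/kg the chances of 0, 1, 2, 3 DLTs in a cohort are 0.1664, 0.4084, 0.3341, 0.0911. The cohort sequences reaching 5/9 without an earlier D or DU are (0,2,3), (0,3,2), (1,1,3) and (1,2,2): 0.00507 + 0.00507 + 0.01520 + 0.04559 = 0.0709. The product is 0.389 × 0.0709 = 2.76%. Every sequence passes through 2/6 or 3/6, both printed E, so the rate is zero if E at the top dose ends escalation.

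Exact enumeration, % of trials naming a DU dose:

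| Part 3A setting | 0.15/0.25 | 0.20/0.27 | 0.25/0.40 | 0.15/0.35 | 0.27/0.45 |
|---|---|---|---|---|---|
| Cohorts of 3, enrolment continues after E | 0.80 | 0.88 | 2.35 | 2.42 | 2.76 |
| Cohorts of 3, E at top dose ends escalation | 0 | 0 | 0 | 0 | 0 |
| Cohorts of 4, either reading of E | 0 | 0 | 0 | 0 | 0 |

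With 3 or 4 evaluable per cohort equally likely and the last cohort cut to fit 12, the rate is 0.2% to 0.8% if enrolment continues after E and about 0.1% to 0.4% if E ends escalation.

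**4. Dependence on the estimator.** With Beta(1,1) means, 0/3 becomes 1/5 = 0.200 (distance 0.090) and 5/9 becomes 6/11 = 0.545 (distance 0.255). The rule then names 0.8 mg/kg. The choice flips once the prior adds more than about 0.08 pseudo-counts per side.

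**5. Monotherapy.** With no DLTs below, a DU dose wins if k/n < 0.54. Up to 13 subjects these are 5/10 (distance 0.230), 6/12 (0.230) and 7/13 (0.268), each under 0.270. Simulating the six Appendix 2 scenarios gave 0.03% to 0.6% with a strict limit of 13, and 0.1% to 1.0% if a cohort begun below 13 may finish. In an independent simulation (40,000 trials per scenario, 0.2% to 1.0%), correct-MTD shares were 22.8, 27.7, 44.1, 49.4, 45.0 and 48.1%, against the plan's 24.7, 28.0, 42.0, 48.3, 44.2 and 46.8%. With Beta(1,1) means no DU dose was named. An assumed steeper curve outside the plan (0.02, 0.02, 0.02, 0.05, 0.10, 0.60) gave 3.8%.

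**The case against.** The strongest reply is that the protocol already answers the point. Sections 3.1.1 and 3.1.3.1 place MTD selection under the mTPI design, that design contains DU, and DU means above the MTD; a dose above the MTD cannot be the MTD. Section 3.1.2 also bars Part 2 doses above the MTD. This stands as evidence of intent. It does not change the selection sentences, which name their candidate set explicitly and leave DU doses in it.

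The Part 3A case is also narrow. It needs a cohort pattern other than fixed fours and an estimator close to raw proportions; with cohorts of 3 it also needs enrolment after a printed E with no higher dose planned. That stands and limits the size.

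Two things cannot be seen: the sponsor's selection program, which may already drop DU doses, and the body of Figure 3.1.1-1, of which only the footnotes were readable in the text used here.

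A reader might infer that Part 1A shows the contradiction in practice, because Section 1.5.1 places 1.6 mg/kg above the MTD while Section 1.5.2 reports DLTs in 4 of 10 treated. The documents do not support that. If all 10 were evaluable, 4/10 is S in Appendix 1, so the table did not close the dose; it was closed by judgement. Section 4.5.1 allows later events to count in defining the MTD, and Section 1.5.1 reports a related Grade 3 pericardial effusion after the second cycle at that dose. The number evaluable at 1.6 mg/kg and the DLT count at 1.2 mg/kg are not given.

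**Conclusion.** The point holds as a wording defect. The selection rule, read literally with observed proportions, can name a dose the protocol has declared above the MTD. In Part 3A the chance is 0.8% to 2.8% under the least favourable setting examined and 0% under several reasonable ones. In the planned monotherapy scenarios it is about 1% or less. These figures rest on the assumptions listed in the check.

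The practical risk is small. Expansion may use an agreed dose below the MTD, and enrolment to an arm is interrupted when drug-related events needing dose modification exceed 31% of treated subjects in Part 3 or 29% in Part 2.

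A reader might go further and infer that the sponsor intends to expand at a closed dose, or that a closed starting dose in Part 3A would be returned as MTD. Neither follows: the intent is plainly the opposite, and Section 3.1.3.1 (a lower dose may be explored) and the nominal level −1 in Appendix 2 deal with a closed starting dose. Severity: minor wording correction.

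**What to change.** In each MTD-determination paragraph (synopsis, Parts 1A, 1B and 3A), in Appendix 2 and in the selection program, define the candidate set as: *among the doses used that were not labelled DU or otherwise declared to exceed the MTD; data from excluded doses stay in the isotonic fit; if no dose remains, no MTD is declared.*

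With this wording, 0/3 and 5/9 returns 0.8 mg/kg. In the Part 3A scenarios with cohorts of 3 and enrolment continuing after E, the share of trials selecting 1.2 mg/kg falls by the 0.8 to 2.8 points tabulated above. The cost is a sentence in each place and one line of code, with no additional subjects.

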### 3.1.3.2 Part 3B (Dose Expansion)

The purpose of the cohort expansion will be to assess preliminary anti-tumor efficacy, expanded safety experience, and PD effects of BMS-986148 in combination with nivolumab. Additional subjects will be treated after the completion of Part 3A, at the MTD or at an alternate dose below the MTD as agreed upon by the BMS Medical Monitor and investigators. Five expansion cohorts will be restricted to these tumor types: 1) mesothelioma, 2) pancreatic, 3) ovarian, 4) NSCLC, and 5) gastric cancer. Enrollment in cohort expansion will be determined by the mesothelin expression of the archived tumor sample (or fresh tumor sample if archived sample is not available).

The enrollment in each combination expansion cohort will also be guided by a Simon 2-Stage design framework (see [Table 8.1-2](#)), exploring efficacy in the

Anti-tumor activity will be assessed initially in approximately 11 to 14 evaluable subjects per tumor type treated in a combination cohort, with the option to stop enrolling in a cohort without an initial anti-tumor activity signal. The number of subjects needed for the Stage 1 review is guided by a Simon 2-Stage design, assuming ORR as shown in [Table 8.1-2](#) for each tumor type with futility boundaries as follows: after Stage 1, if 0 or 1 of the first 11 evaluable subjects in the gastric or pancreatic cohorts, 0 or 1 of the first 14 in the evaluable ovarian cohorts,  $\leq 2$  of the first 12 with mesothelioma cohort, or  $\leq 1$  in the first 10 in the NSCLC cohort show clinical activity, enrollment in the cohort meeting criteria may be stopped.

Evaluation of efficacy will occur independently in each tumor cohort. At the time of the Stage 1 efficacy assessment, subjects will be enrolled to include sufficient numbers in both the populations to allow an initial (Stage 1) efficacy assessment. If there is a lack of signal for preliminary efficacy (number of responders not exceeding the boundary), and after evaluation of all available data, enrollment may be stopped in that population. Otherwise, additional subjects will be treated in Stage 2 for the population in which there was an initial signal.

As described for the monotherapy expansion, the above numbers are approximate, and enrollment may continue during the evaluation of the interim data.

Of note, fresh tumor biopsy at screening and on treatment will be mandatory for 10 ovarian cancer subjects and for 10 gastric cancer subjects enrolled in Part 3B. Fresh tumor biopsy at screening and on-treatment will be optional for subjects with other indications.

Safety monitoring of subjects enrolled in the Part 3B portion of the study will be the same as that conducted during the dose escalation portion. During Part 3, if in a given arm the combined incidence of study drug-related AEs that require dose modification exceeds 31% (of treated subjects), then further enrollment to that arm will be interrupted, and the findings will be discussed between the BMS Medical Monitor and investigators. An agreement will be reached as to whether a lower dose or an alternate dose schedule of BMS-986148 in combination with nivolumab should be examined or whether any additional treatment guidelines should be implemented prior to enrollment of additional subjects on study.

### **3.1.4 Administration of Additional Treatment Cycles (Part 3)**

In Part 3 of this study, all subjects will be treated for 24 weeks (up to 8 cycles) of BMS-986148 in combination with nivolumab unless criteria for study drug discontinuation are met earlier ([Section 3.5](#)). All subjects completing approximately 24 weeks of study therapy with ongoing disease control (CR, PR, or SD) may be eligible for an additional 24 weeks of study therapy at the originally assigned dose regimen in both escalation and cohort expansion beyond the initial 24 weeks, on a case-by-case basis, after careful evaluation and discussion with the BMS Medical Monitor to determine whether the benefit/risk ratio supports administration of further study therapy. Upon completion of 24 weeks of study therapy (or up to a maximum of 48 weeks if applicable), all subjects will enter the clinical/safety Follow-up period.

Following every 2 treatment cycles (every 6 weeks [Q6W] for Part 3), the decision to treat a subject with additional cycles of study therapy will be based on radiological tumor assessments (initial evaluation performed at baseline and every 2 cycles or every 6 weeks). Treatment decisions related to subject management will be based exclusively on Response Evaluation Criteria in Solid Tumors (RECIST) version 1.1 or Modified RECIST for malignant pleural mesothelioma (see [Appendix 4](#)). Assessments of PR and CR must be confirmed at least 4 weeks following initial assessment. Subjects with an overall response of CR, PR, or SD will continue therapy until they develop CR confirmed, develop progressive disease, experience clinical deterioration, develop AEs requiring discontinuation of treatment, or withdraw consent. Individual subjects with confirmed CR will be given the option to continue BMS-986148 in combination with nivolumab on a case-by-case basis after specific consultation and agreement between the investigator and BMS Medical Monitor in settings where benefit/risk justify continuation of study therapy.

### **3.1.5 Treatment Beyond Progression**

Treatment beyond progression in Part 3 of this study may be allowed in select subjects with initial RECIST version 1.1 or Modified RECIST for malignant pleural mesothelioma-defined progressive disease after discussion and agreement with the BMS Medical Monitor that the benefit/risk assessment favors continued administration of study therapy (eg, subjects are continuing to experience clinical benefit as assessed by the investigator, tolerating treatment, and meeting other criteria specified in [Section 4.6](#)).

### **3.1.6 Follow-Up**

Subjects who develop toxicity requiring discontinuation of treatment will enter the Follow-up period. Subjects should be seen in follow up at least every 30 days, until the AE has resolved to baseline, stabilized, or been deemed irreversible. After completion of the Follow-up period, subjects will then enter the Survival Follow-up period. During this period, clinic visits or telephone contact every 3 months will be performed to assess survival status. The duration of this period is detailed in [Section 3.1](#). Subjects in Survival Follow-up who have progression of disease will be eligible to receive anti-cancer therapy as appropriate.

